1.0 ABSTRACT

Although hematopoietic stem cell transplantation (HSCT) is the only therapy that can cure patients with the myelodysplastic syndrome (MDS), and HSCT has long been the standard of care for younger patients with high-risk disease, the procedure has been traditionally withheld from older patients due to concerns about excessive toxicity and limited underlying overall survival. More recently, however, HSCT with reduced-intensity conditioning (RIC) has been increasingly offered to older patients with the syndrome, a clinical picture that is complicated by the introduction of non-HSCT disease-modifying treatments for MDS such as the DNA methyltransferase inhibitors. We propose an observational study enrolling high-risk MDS patients who are fit enough to undergo RIC HSCT but whose HLA and donor status is unknown at baseline. Whether or not enrollees eventually go on to HSCT—indeed, many will not, due to factors such as lack of a suitable donor or rapid progression of disease—all will be followed for outcomes such as overall survival, progression free survival, and quality of life. Our protocol will generate much-needed comparative outcomes data for older patients with high-risk MDS, and has the potential to greatly influence how the disorder is treated in the United States.

2.0 BACKGROUND AND SIGNIFICANCE

The myelodysplastic syndromes (MDS) are a group of hematopoietic stem cell disorders characterized by ineffective hematopoiesis and a tendency to transform to leukemia. They range in clinical severity from incidentally-found cases manifesting with mild anemia, to highly symptomatic cases characterized by severe anemia, neutropenia and/or thrombocytopenia. These latter cases are often accompanied by hemorrhage, infection and rapid mortality, and are thus the focus of most MDS treatments, including HSCT. Despite recent advances in treatment and classification, until recently little was known about the epidemiology and patterns of care for patients with MDS in the United States.¹ Indeed, MDS was only added to the National Cancer Institute's Surveillance Epidemiology and End Results (SEER) program in 2001, and reliable incidence rates (2001-2003) were only recently reported: 3.4 cases per 100,000, with a male predominance (4.5 for males versus 2.7 for females) and three-year overall survival of 45%.²⁻³ Data on patterns of care for MDS patients is also limited, although it is known that the newer WHO classification system⁴ (as compared to the older FAB system) has become widely-adopted in clinical practice.⁵ One study reported the results of a survey among US hematologists,⁶ finding that fewer MDS patients with lower-risk disease were transfusion-dependent, a majority received erythropoiesis-stimulating agents (ESAs), and only a small percentage of patients had had or were being considered for HSCT.⁷

This last finding is provocative, as HSCT remains the only curative option for MDS. Indeed, HSCT has a long and successful history in management of these hematologic disorders, using both ablative and RIC regimens.⁸⁻²⁴ A recent evidence-based review published under the aegis of the American Society of Blood and Marrow Transplantation was supportive of the role of HSCT in the management of MDS.²⁵ Moreover, the introduction of RIC regimens has greatly expanded the utility of HSCT in older and sicker patients by reducing the risk of regimen-related toxicity.²⁶⁻³² For example, Kroger and associates reported on 26 patients with MDS or secondary AML (median age = 60; range 44 to 70) who were transplanted with RIC with cells from related (n=6) or unrelated (n=20) donors. Transplant-related mortality was 28%, and the two-year

estimate overall survival rate was 36%.²⁹ A Spanish trial reported results on 37 patients (median age = 57; range 22 to 66) with MDS or AML transplanted from HLA-identical siblings following a RIC regimen. The one-year transplant-related mortality and relapse-free survival were 5% and 66%, respectively. In our group, we have found similar outcomes in patients treated with RIC and myeloablative regimens. For example, we reviewed 136 patients with advanced AML and MDS undergoing allogeneic HSCT, comparing 39 patients receiving RIC HSCT to 97 patients receiving myeloablative HSCT. Patients receiving RIC were at high risk for treatment-related complications given that they were older, 57 vs 43 years ($P < .001$), and more likely had received previous or myeloablative transplantation (54% vs 2%; $P < .0001$). Still, Cox regression analysis showed that the intensity of the conditioning regimen had no effect on either overall survival or progression free survival, suggesting that RIC is a reasonable alternative for patients with advanced MDS or AML at high risk for complications with myeloablative HSCT.³³

Despite these promising preliminary results, until recently, concerns regarding morbidity and mortality related to even RIC HSCT limited its application in older patients (60 to 75) with MDS, especially given the lack of rigorous comparative outcomes data from a study including patients both with and without HSCT. Perhaps due to this fact, earlier this year, the Centers for Medicare & Medicaid Services (CMS)—the main health insurer for adults 65 and older in the United States—posted their controversial decision on coverage of HSCT for Medicare patients with MDS. In the decision, CMS disallowed coverage for HSCT, but stated that the current data from younger patients, especially with regard to RIC HSCT, is promising enough to provide for some coverage under the Coverage with Evidence Development process (§1862(a) (1) (E) of the Social Security Act. This allows for Medicare patients with MDS to receive HSCT provided that the HSCT is performed in the context of a prospective clinical study comparing Medicare patients with MDS who receive HSCT to similar Medicare patients with MDS who do not. In part to address this challenge, the aim of this current protocol is to prospectively examine post-RIC HSCT outcomes in those patients aged 60 to 75 with MDS (which would include Medicare beneficiaries aged 65 to 75) to determine whether these outcomes are similar to those patients with MDS aged 60 to 75 who do not undergo HSCT, but who both have disease severe enough as well as a health status good enough they would also be eligible for RIC HSCT.

3.0 STUDY OBJECTIVES

3.1 Primary Objective

To prospectively compare the overall survival (OS) of patients aged 60-75 who undergo HSCT for MDS (Group A) to that of patients aged 60-75 who do not undergo HSCT (Group B) but who have disease of sufficiently high enough risk to warrant HSCT and who are also fit enough to undergo the procedure (**primary outcome**).

3.2 Secondary Objectives

1. To prospectively compare the progression-free survival (PFS) of patients in Group A to that of patients in Group B as defined above (**secondary outcome**).
2. To prospectively compare changes in the quality of life (QoL) from baseline to two years of patients in Group A to that of patients in Group B as defined above (**secondary outcome**).

3. To assess the potential association of patient- and disease-specific factors—including International Prognostic Scoring System (IPSS) score, WHO-based Prognostic Scoring System (WPSS) score, number of cytopenias, transfusion dependence, disease duration at baseline, prior therapies and age at HSCT—with the primary and secondary outcomes.

4.0 STUDY POPULATION

Eligible patients will be 60 to 75 years old with a diagnosis of MDS or related disorder (eg, MDS/MPD or CMML) who have disease that is advanced enough to warrant RIC HSCT (defined by high-risk cytogenetics,³⁴ int-2 or high-risk on IPSS³⁵ or transfusion dependence as defined by WPSS³⁶) and who are physically fit enough to undergo RIC HSCT as assessed by pre-determined measures of organ function. Patients whose baseline donor status is known will be excluded; however, knowledge of HLA status is allowed as long as a donor search has not been performed.

4.1 Inclusion Criteria

1. Histologically-confirmed diagnosis of:
 - a. Primary or secondary MDS using the World Health Organization (WHO) 2008 classification:
 - i. Refractory cytopenia with unilineage dysplasia
 1. Refractory Anemia (RA)
 2. Refractory Neutropenia (RN)
 3. Refractory Thromobucytopenia (RT)
 - ii. Refractory Anemia with Ring Sideroblasts (RARS)
 - iii. Refractory Cytopenia with Multilineage Dysplasia (RCMD)
 - iv. Refractory Anemia with Excess Blasts-1 (RAEB-1)
 - v. Refractory Anemia with Excess Blasts-2 (RAEB-2)
 - vi. MDS with isolated del (5q)
 - vii. MDS-Unclassified (MDS-U)
 - b. Another of the following related disorders:
 - i. Chronic Myelomonocytic leukemia (CMML)
 - ii. Myelodysplastic/myeloproliferative neoplasm, unclassifiable (MDS/MPD-U)
2. Age 60 to 75 years
3. Intermediate-2 or High-Risk IPSS

OR

Secondary MDS (any karyotype)

OR

Documented non-IPSS intermediate- or poor-prognosis karyotype⁴³ including:

- i. del(11q)

- ii. +8
- iii. t(11q23)
- iv. Rea 3q
- v. +19
- vi. 3 or greater abnormalities
- vii. del(7q)
- viii. -5
- ix. t(5q)

OR

Documented significant cytopenia for at least four months prior to enrollment, defined by the following criteria:

- a. *Red Blood Cell (RBC) Transfusion Dependence*: four or more units of RBC transfusions within an eight-week period for symptomatic anemia with hemoglobin of ≤ 9.0 g/dL; **OR**
- b. *Severe Anemia*: average of two or more hemoglobin values ≤ 8 g/dL within an eight-week period not influenced by RBC transfusions (i.e., must be seven days post transfusion); **OR**
- c. *Severe Thrombocytopenia*: average of two or more platelet counts $\leq 50 \times 10^9/L$ within an eight-week period not influenced by platelet transfusions (i.e., must be at least three days post- transfusion) or a clinically significant hemorrhage requiring platelet transfusions within the prior four months; **OR**
- d. *Severe Neutropenia*: average of two or more absolute neutrophil counts (ANC) ≤ 500 within an eight-week period, or a clinically significant infection requiring IV antibiotics in the setting of ANC ≤ 1000 within the prior four months.

4. Eastern Cooperative Oncology Group (ECOG) performance status of 0, 1 or 2.

5. Adequate organ function to permit RIC HSCT as indicated by the following:

- a. Serum bilirubin ≤ 2.5 mg/dL (except when Gilbert's syndrome or MDS-related hemolysis suspected).
- b. AST and ALT ≤ 2.5 times the upper limit of normal (ULN).
- c. Serum creatinine ≤ 2.0 mg/dL
- d. Seemingly sufficient baseline cardiac function to undergo HSCT (no echocardiogram required).
- e. Seemingly sufficient baseline pulmonary function to undergo HSCT (no pulmonary function tests required).
- f. Seemingly sufficient neuro-psychiatric function to undergo HSCT (no specific neuro-psychiatric evaluation required).

6. Willingness to undergo HLA-typing and consider subsequent HSCT.
7. Willingness and ability to give informed consent.

4.2 Exclusion Criteria

1. Known baseline conversion to AML (eg, $\geq 20\%$ peripheral or marrow blasts).
2. Knowledge of potential donor status at study entry. Of note, knowledge of HLA status WITHOUT a related or unrelated search is allowed.
3. History of prior malignancy within the past year, except for adequately-treated carcinoma in situ of uterine cervix, basal cell or squamous cell skin cancer.
4. Any severe concurrent disease, infection, or comorbidity that, in the judgment of the principal investigator, would make the patient inappropriate for HSCT at the time of study entry.
5. Psychiatric disorders including dementia that would preclude obtaining informed consent or the ability to participate in an ongoing research study.

5.0 STUDY DESIGN AND METHODS

5.1 Data Collection

Data for this study will be collected using the existing mechanisms of the Dana-Farber/Harvard Cancer Center (DF/HCC) Leukemia Clinical Research Information Systems (Leukemia CRIS) for baseline data (all study participants). For patients who do not go on to HSCT, Leukemia CRIS will be used to collect their outcomes, while HSCT patients will have outcomes collected in the Center for International Blood and Marrow Transplant Research Stem Cell Therapeutic Outcomes Database (CIBMTR SCTOD). Leukemia CRIS is a state-of-the-art information infrastructure for hematologic oncology at the DF/HCC, developed to link clinical outcomes to blood and tissue samples, and to lay the foundation for innovative pilot studies and health services research. The database has been accruing data since January of 2006. Patients in Leukemia CRIS have baseline information and a new patient survey entered at 3 months; they are then assessed for outcomes every 6 months for 3 years. After 3 years, their records are updated for outcomes once per year. Note that baseline IPSS, WPSS and entry criterion (eg, histology, cytogenetics, or transfusion requirements), or as well as eventual HLA status and donor status will be added to Leukemia CRIS data screens and captured for MDS-TAO patients. Also, QoL will be assessed at baseline and two years with the EORTC-30,³⁷ a validated quality of life instrument, as well as the QUALMS-1, an MDS-specific quality of life instrument being validated by [name] under OHRS protocol 13-346.

5.2 Methods of Procedure

A dedicated clinical research assistant will work with the hematologic oncology new patient coordinators at the DF/HCC member institutions (Dana-Farber Cancer Institute (DFCI), Beth

Israel Deaconess Medical Center (BIDMC) and Massachusetts General Hospital (MGH)) to identify high-risk MDS patients that may be eligible for the study. The transplant and non-transplant MDS physicians will be ultimately responsible for identifying patients who are eligible for MDS-TAO; in addition, as all MDS patients followed at the DF/HCC are eligible for the Leukemia CRIS database, the research assistant and the Principal Investigator will also perform periodic reviews of MDS patients seen at the DF/HCC to retroactively assess eligibility and contact the appropriate physician to encourage that physician to enroll appropriate patients. Of note, the point of contact for patient enrollment will always be the treating physician.

Once enrolled, all study patients will be followed for the primary and secondary outcomes listed above, with assessments in step with those in the Leukemia CRIS system (baseline and every 6 months for 3 years; then yearly). A difference is that MDS-TAO patients will be followed on the same schedule whether or not they continue to receive their care at DF/HCC (Leukemia CRIS does not follow patients that are only seen for one-time consultation at DF/HCC). The investigators understand that this will require a different informed consent, and more resources (eg, another clinical research assistant) to obtain and abstract outside hospital records. Also, all MDS-TAO enrollees will be given the EORTC-30 to take home and mail back (if they have not already done it as part of their Leukemia CRIS new patient survey) at baseline and again at two years, regardless of HSCT status or whether or not they continue to be followed at DF/HCC. All enrollees will also be asked to complete the QUALMS-1 instrument. Finally, as above, if any patient goes on to RIC HSCT, his or her data—including outcomes—will be collected in the CIBMTR SCTOD.

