6.6 Secondary Outcomes

Secondary outcomes include PFS and changes in self-reported QoL. PFS is defined as time from enrollment until evidence of progression to acute leukemia (time until increase in marrow or peripheral blasts to >20%). QoL will be assessed via changes between baseline and two-year assessments on the EORTC-30 and QUALMS-1. We also plan baseline assessment of IPSS and WPSS, number of cytopenias, transfusion dependence, disease duration at baseline, prior therapies and age at HSCT. Of note, we have not based our power calculations on these outcomes and covariates due to their exploratory nature.

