APPENDIX B: New Patient Survey for Leukemia CRIS, including EORTC-30

APPENDIX C: QUALMS-1 Quality of Life Instrument

APPENDIX D: Consent Form for MDS-TAO

Hematologic Oncology New Patient Survey

Patient Name	Age	D.O.B.
DFCI MRN	BWH MRN	MGH MRN
Appt Provider	Appt Date/Time	

Please fill out this form and return it to the
MAIN RECEPTION DESK

Please complete this form as thoroughly as possible. This information will help your health care providers to develop a plan of care tailored to your needs.

Thank you.

REASON FOR SEEKING CARE**Where were you first diagnosed with your blood disorder?**

Select ONE.

- Emergency Room
- Hospital
- Hematologist/Oncologist's office
- Primary Care Physician
- Other physician office
- Other

Have you seen another physician for your current blood disorder?

- No
- Yes

If yes, what type of physician(s) have you seen previously for the treatment or evaluation of your current blood disorder?

Select ALL that apply.

- Medical oncologist (treats with chemotherapy / medicines)
- Primary care physician
- Radiation oncologist (treats with radiation)
- Other (Please specify: _____)

REASON FOR SEEKING CARE (continued)

Have you received any prior treatments for your blood disorder?

No Yes

If yes, what prior treatments have you received?

Select **ALL** that apply.

- Chemotherapy
- Radiation therapy
- Surgery
- Vaccine therapy
- Other (Please specify: _____)

Who recommended that you to come to DFCI/MGH for consultation?

Select **ALL** that apply.

- Children
- Friend
- Internet
- My oncologist
- My primary care physician
- Self
- Spouse
- Other family
- Other (Please specify: _____)

Why are you coming to clinic today?

Select **ALL** that apply.

- To find out whether I have a blood disorder
- To see if I'm eligible for a clinical trial
- To find out if there are any new treatments available
- Other (Please specify: _____)

Do you expect to receive your ongoing care at DFCI/MGH?

Select **ONE**.

- No- I'm here for a second opinion
- Yes
- Not sure

REASON FOR SEEKING CARE (continued)

Outside of a multivitamin do you REGULARLY do other complementary/nontraditional/alternative therapies?

No Yes

If yes, which therapies? Select **ALL** that apply.

 Acupressure	 Macrobiotics	 Tai Chi or Chi Gong
 Acupuncture	 Massage	 Yoga

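### An earlier new-patient survey of any age can serve as the EORTC-30 baseline, so for patients enrolled later the quality-of-life change can start before study entry

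*Combined protocol and SAP*

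**What the plan says.** Section 3.2 makes the change in quality of life from baseline to two years a secondary objective. Section 6.6 defines it: "QoL will be assessed via changes between baseline and two-year assessments on the EORTC-30 and QUALMS-1". Section 5.1 gives the same two time points ("QoL will be assessed at baseline and two years with the EORTC-30") but does not define baseline by a date or a window.

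Section 5.2 describes collection. Enrollees take the EORTC-30 home and mail it back at baseline and at two years, but the baseline form is given only "if they have not already done it as part of their Leukemia CRIS new patient survey". The QUALMS-1 has no such exception: "All enrollees will also be asked to complete the QUALMS-1 instrument".

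Section 5.2 also describes two ways into the study. New-patient coordinators and treating physicians identify candidates, and in addition the research assistant and Principal Investigator periodically review MDS patients already seen "to retroactively assess eligibility and contact the appropriate physician".

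The appendix list shows that the intake survey carries one instrument and not the other: "APPENDIX B: New Patient Survey for Leukemia CRIS, including EORTC-30" and, separately, "APPENDIX C: QUALMS-1 Quality of Life Instrument". On timing, Section 5.1 says: "Patients in Leukemia CRIS have baseline information and a new patient survey entered at 3 months".

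**The concern.** The intake survey belongs to a patient's first clinic visit, not to consent for this study. A change score meant to describe the two years after study entry can therefore take its starting value from an earlier point, with no limit on how much earlier. For such a patient the EORTC-30 change mixes what happened before entry with what happened after it. Overall survival and PFS, by contrast, run from study entry or enrollment (Sections 6.4 and 6.6).

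The comparison of Group A with Group B on this outcome is at stake. It would be distorted if early surveys were more common, or older, in one group and quality of life was changing before entry. Most EORTC-30 items ask about the past week, so a value missed at enrollment cannot be recovered later.

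**Working it through.** The plan states no figure for this outcome that could be reproduced: Section 6 gives no quality-of-life effect size, standard deviation or power. The check is a reading of the text followed by simple arithmetic.

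**1. Is the survey an intake form?** Yes. The form in Appendix B asks why the patient has come to clinic and is returned at reception. It contains all the EORTC-30 items: 5 + 23 + 2 = 30. Of these, 23 + 2 = 25 refer to the past week. It therefore records the patient's state around that visit.

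**2. Can enrollment come later than the survey?** Yes. The retrospective review in Section 5.2 is by design a route for patients already seen. Section 4.1 also has an entry route requiring at least four months of documented cytopenia, which some patients may meet only after their first visit.

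**3. Is the gap limited anywhere?** No. No section sets a maximum interval, requires the form to be repeated at entry, or says whether the two years run from the survey or from enrollment. The three-month remark in Section 5.1 could mean when the survey is completed or when it is keyed in, so a database date may not be the completion date.

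**4. What interval does the score cover?** Let L be the months from survey to enrollment.

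- Two-year form timed from enrollment: the EORTC-30 change spans 24 + L months. For assumed L = 0, 3, 6 and 12 this is 24, 27, 30 and 36 months. A QUALMS-1 completed at enrollment spans 24.
- Two-year form timed from the survey: the span is 24 months, but only 24 − L of them follow study entry.

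Either way the score starts before entry whenever L > 0.

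**5. What could this do to the group difference?** Suppose quality of life falls by d points per month before entry, and a share p of each group's scored patients has an early survey. With d and L common to both groups, the error in the difference (positive favors Group A) is (p_B − p_A) × d × L. Every input below is assumed; none is in the documents.

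- Error per affected patient, d = 0.5 to 1 and L = 6 to 12: 0.5 × 6 = 3 to 1 × 12 = 12 points.
- p_B = 30%, p_A = 10%: 0.20 × 3 = 0.6 to 0.20 × 12 = 2.4 points in favor of Group A.
- Equal shares: 0.
- Shares reversed: −0.6 to −2.4 points.

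The illustration thus runs from −2.4 to +2.4, and the documents do not fix even the sign.

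**6. Who supplies a two-year score?** Only survivors. Under the Section 6.4 curves, with t in months, S_A(24) = 0.19 + 0.4 × 2^(−2.4) + 0.41 × 2^(−1.2) = 0.444 and S_B(24) = 2^(−24/18) = 0.397. More than half of each group would have no two-year score, so the shares in step 5 would have to hold among survivors, on which the documents are silent.

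**The case against.** The strongest defense is that the waiver does no harm for many patients. Recruitment runs partly through new-patient coordinators, and the survey is the new-patient form; where a patient enrolls at that visit, survey and study entry coincide. The retrospective review is an added route. The exclusion of patients with known donor status (Section 4.2) further limits late enrollment of those already being worked up for transplant. All of this stands, and it confines the problem to a subset. It does not remove the problem, because nothing limits the waiver to same-visit enrollment.

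A reader might infer three stronger things that the documents do not support.

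- *That the error favors transplant.* The argument would be that patients found late, still without a donor search, tend to end in Group B. But unknown donor status is an entry condition for everyone, and no section links the route of entry to later group.
- *That the two instruments can no longer be compared.* Sections 6.6 and 6.7 list both as measures of quality of life and plan no comparison between them.
- *That the QUALMS-1 baseline is certain to fall at study entry.* It is asked of enrollees, which makes completion at or after enrollment the natural reading, but no date is fixed for it either.

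It is also fair to say that Section 6.6 treats these outcomes as exploratory and bases no power on them.

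**Conclusion.** The point holds in a limited form. As written, Section 5.2 allows the EORTC-30 change to begin before study entry, by an unlimited interval, for enrollees whose intake survey predates enrollment. For them the change spans 24 + L months if the follow-up form is timed from enrollment. The number of such patients and the distribution of L are not given.

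No bias of a particular size or direction has been shown. The ±2.4 points above illustrate what assumed inputs would produce; with equal lag, drift and shares the bias is zero. Even then, change scores within a group would cover unequal intervals.

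The consequence is confined to an exploratory secondary outcome. Overall survival, PFS and the sample size do not depend on it. The change is worth making because it is cheap and the data cannot be reconstructed afterwards.

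**What to change.** In Section 5.2, replace the open-ended waiver with a dated rule:

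- Both the EORTC-30 and the QUALMS-1 are completed within a short, fixed window around enrollment. The investigators should set its length in advance. Four weeks is one possibility, but the documents give no basis for a particular figure. Section 6.4 expects about 4–6 months from enrollment to transplant, so a window of a few weeks should normally fall before it.
- A previous Leukemia CRIS survey counts as the EORTC-30 baseline only if completed inside that window; otherwise the form is repeated.
- The completion date of each form is recorded, separately from the data-entry date.
- The two-year assessment is timed from enrollment for both instruments.

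For anyone already enrolled under the waiver, the appointment date on the survey header could probably be used to measure the gap, and a sensitivity analysis could leave out those with surveys outside the window.

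The cost is a few sentences in Section 5.2 and one repeated 30-item form for some enrollees.
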